### 2.2.3 Exploratory Objectives and Endpoints

Objective	Endpoints
1. To assess the immune response elicited by the ARCT-2303 vaccine against a panel of SARS-CoV-2 strains, as measured by VNA	SARS-CoV-2 neutralizing antibody responses with a panel of historical and new emergent SARS-CoV-2 strains on Days 1 and 29 in a subset of: 
 
• Standalone ARCT-2303 group recipients (Group 2a and/or 2b)
 
• Standalone QIV group recipients (Group 3a and/or 3b)
 

2. To assess the immunogenicity of influenza vaccine(s) when administered with or without ARCT-2303 as measured by microneutralization assay (in a subset of participants)	Microneutralization (MN) titers against influenza vaccine strains on Day 1 and Day 29, in: 
 
• Co-admin group recipients (a subset of participants from Group 1a and/or 1b)
 
• Standalone QIV group recipients (a subset of participants from Group 3a and/or 3b).
 

### 2.3 Sample Size

A total sample size of approximately 1680 participants (1200 participants 18 to 64 years of age, and 480 participants  $\geq 65$  years of age), and a sample size of 385 participants of study ARCT-154-J01 (PPS-1) is proposed for the study objectives. A full discussion of the sample size calculation can be found in the Section 13.

## 2.4 Randomization

After signing the informed consent form (ICF) each participant will be given a Participant ID according to the screening order. On Day 1, following confirmation of eligibility, a randomization number will be assigned, and participants will be allocated to treatment using an interactive response technology (IRT), Medidata Rave Randomisation and Trial Supply Management (RTSM).

On Day 1, within each age cohort (A and B), participants will be randomly assigned at a 1:1:1 ratio into three study groups:

### ***Cohort A (participants 18 to 64 years of age; approximately 1200 participants)***

- Group 1a (ARCT-2303/Flucelvax Quadrivalent, N=400): participants will receive one dose of ARCT-2303 and one dose of Flucelvax Quadrivalent (opposite arms) on Day 1, and one dose of placebo on Day 29.
- Group 2a (ARCT-2303, N=400): participants will receive one dose of ARCT-2303 and one dose of placebo (opposite arms) on Day 1, and one dose of Flucelvax Quadrivalent on Day 29.
- Group 3a (Flucelvax Quadrivalent, N=400): participants will receive one dose of Flucelvax Quadrivalent and one dose of placebo (opposite arms) on Day 1, and one dose of ARCT-2303 on Day 29.

### ***Cohort B (participants ≥65 years of age; approximately 480 participants)***

- Group 1b (ARCT-2303/Fluad Quadrivalent, N=160): participants will receive one dose of ARCT-2303 and one dose of Fluad Quadrivalent (opposite arms) on Day 1, and one dose of placebo on Day 29.
- Group 2b (ARCT-2303, N=160): participants will receive one dose of ARCT-2303 and one dose of placebo (opposite arms) on Day 1, and one dose of Fluad Quadrivalent on Day 29.
- Group 3b (Fluad Quadrivalent, N=160): participants will receive one dose of Fluad Quadrivalent and one dose of placebo (opposite arms) on Day 1, and one dose of ARCT-2303 on Day 29.

Randomization will be stratified based on their COVID-19 vaccination history:

- 1) Total number of COVID-19 vaccine doses
  - a. 3 doses
  - b. 4+ doses
- 2) Composition of the last booster dose
  - a. original strain
  - b. bivalent/XBB1.5
  - c. unknown.

The stratification groups are designed to be balanced based on actual N of participants in each group, and the maximum percent of participants in each stratification group is not pre-specified.

## 2.5 Blinding and Unblinding

This study will be observer-blind.

Due to the visual differences between the study vaccines, the participants will be blinded before receiving the study vaccinations. An unblinded dosing team, not involved with study participant's evaluation, will prepare and administer the study vaccine doses. The study vaccine syringe will be opacified to avoid unblinding of the participant.

The administration of the study vaccine will also be performed behind a closed curtain to ensure that the other blinded staff members do not become unblinded. The investigative study center personnel, as well as the sponsor personnel involved in the monitoring or conduct of the study, will be blinded to the study vaccine code.

The laboratories in charge of immunogenicity and safety testing will also be blinded, so associating the sample with an assigned treatment or study visit will not be possible.

The treatment code should be broken only if the investigator/physician in charge of the participant feels that the case cannot be treated without knowing the identity of the study vaccine. Except in cases of medical necessity, a participant's treatment should not be unblinded without the approval of the sponsor. If unblinding should occur (by either accidental unblinding or emergency unblinding) before completion of the study, the investigator must promptly contact the sponsor or designee and document the date and reason that the blind was broken in the source documentation and eCRF. Instructions regarding emergency unblinding will be provided to the investigator.

All personnel involved in the study will remain fully blinded until the first final analysis (Day 57). For Day 57 analysis, immunogenicity and safety data will be reported on a group level; no individual listings will be generated. Access to participant-level information about study groups will be restricted to specified personnel involved in the statistical analysis.

The blinded site staff, CROs (not involved in the statistical analysis), and sponsor representatives (not involved in the statistical analysis/writing of CSR) will remain blinded until final database lock.

### 3 STATISTICAL CONSIDERATIONS

Statistical analyses and generations of Tables, Listings and Figures (TLFs) will be handled and processed per the sponsor's representative (Cytel) Standard Operating Procedures (SOPs), which are written based on the principles of Good Clinical Practice (GCP).

#### 3.1 General Considerations

Data collected on the electronic case report form (eCRF) will be presented in the data listings for the second analysis (study end) and will be listed and sorted by cohort, treatment group, participant number and visit, where applicable. No individual listings will be generated at the first analyses (Day 57).

All safety and descriptive summaries will be presented by the treatment group and nominal visit/time point (where applicable). All disposition and concomitant medication descriptive summaries will be presented by treatment group.

Unless otherwise stated, the following methods will be applied:

- **Continuous variables**: Descriptive statistics will include the number of non-missing values (n), arithmetic mean, standard deviation (SD), median, minimum, and maximum values. The minimum and maximum values will be displayed to the same decimal precision as the source data, the arithmetic mean, SD, and median values will be displayed to one more decimal than the source data for the specific variable. 95% Confidence Intervals (CIs), mean differences (among treatments and from baseline) and least-square (LS-Means) values will be displayed to one more decimal than the source data for a specific variable. The appropriate precision for derived variables will be determined based on the precision of the data on which the derivations are based, and statistics will be presented in accordance with the above-mentioned rules. For source data with > 5 decimals, rounding to a maximum of 3 decimals will be performed.
- **Categorical variables**: Descriptive statistics will include counts and percentages per category. The denominator in all percentage calculations will be the number of participants in the relevant analysis population with non-missing data, unless specifically stated otherwise. Percentages will be displayed to one decimal place. Proportions will be displayed to 3 decimal places. 95% Confidence Intervals (CIs), differences, and other categorical parameters will be displayed to one decimal place for percentages. 95% Confidence Intervals (CIs) and differences in proportions will be displayed to 3 decimal places.
- **Repeat/unscheduled assessments**: Only values collected at scheduled study visits/time points will be presented in summary tables. If a repeat assessment was performed, the result from the original assessment will be presented as the result at the specific visit/time point (early termination visits will not be summarized). All collected data will be included in the data listings.
- **Duplicate entries in eDiary**: For duplicate daily entries in the electronic diary with at least one different value collected between 2 entries, the last data entered will be considered for the analysis (rule established before any planned analysis).
- **Assessment windows**: All assessments will be included in the data listings and no visit windows will be applied to exclude assessments that were performed outside of the protocol specified procedure windows. For safety summaries (where applicable), the table below defines the analysis time windows that correspond to the targeted visit.

Visit (target day)	Visit window (days)
Study Day 1: Screening and Vaccination 1	-7
Study Day 29: Follow-up Visit 1 and Vaccination 2	± 3
Study Day 57: Follow-up Visit 2	± 3
Study Day 91: Safety Call	± 7
Study Day 181: Final Visit (EOS)	± 7

- Result display convention: Results will be center aligned in all summary tables and listings. Participant identifiers visit and parameter labels may be left-aligned if required.
- Date and time display conventions: The following display conventions will be applied in all outputs where dates and/or times are displayed:

Date only: YYYY-MM-DD

Date and time: YYYY-MM-DD HH:MM

If only partial information is available, unknown components of the date or time will be presented as 'NK' (not known), i.e., '2016-NK-NK'. Times will be reported in military time.

### 3.2 Key Definitions

The following definitions will be used:

- Baseline: The baseline value is defined as the last available valid (quantifiable continuous or categorical value), non-missing observation for each participant prior to first study vaccine administration. If an assessment is taken on the day of first study vaccine administration, but the time is not available, this assessment will be considered for baseline assessment. Repeat and unscheduled assessments will be included in the derivation of the baseline values.
- Change from Baseline: The change from baseline value is defined as the difference between the result collected/derived at a post-baseline visit/time point and the baseline value.

The change from baseline value at each post-baseline visit/time point will be calculated for all continuous parameters using the following formula:

$$\text{Change from Baseline Value} = \text{Result at Visit/Time Point} - \text{Baseline Value}$$

The change from baseline value will only be calculated if the specific post-baseline visit/time point result and the baseline value for the parameter are both available and will be treated as missing otherwise.

- Study day: The study day of an event is defined as the relative day of the event starting with the date of the first study vaccine administration (reference date) as Day 1 (there will be no Day 0).

The study day of events occurring before the first study vaccine administration will be calculated as:

$$\text{Study Day} = (\text{Date of Event} - \text{Date of First Study Vaccine Administration})$$

For events occurring on or after Day 1, study day will be calculated as:

$$\text{Study Day} = (\text{Date of Event} - \text{Date of First Study Vaccine Administration}) + 1$$

Study days will only be calculated for events with complete dates and will be undefined for events that are 'Ongoing' at the time of database lock (either Day 57 or end of study).

Relative days compared to an alternative reference point will be calculated similarly, but the alternative starting reference start date will be used instead of the date of the first study vaccine dosing.

- Prior Medications: Prior medications are defined as any medication stopped prior to the first administration of the study vaccine.
- Concomitant Medications: Concomitant medications are defined as any medication (other than the study vaccine) that was used at least once after the first administration of the study vaccine. Medications that were stopped on the same date as the first study vaccine administration will be defined as concomitant medications. If a clear determination cannot be made (partial medication end dates) the medication will be classified as concomitant
- Treatment Emergent Adverse Events (TEAEs) are defined as adverse events that occurred following the first administration of study medication. Adverse events without enough evidence to identify whether it occurred before or after the first administration will be considered as a TEAE.

### 3.3 Inferential Analyses

#### 3.3.1 Hypotheses

A sequential, unidirectional testing procedure is planned to account for multiplicity, i.e., hypotheses in step 2 will only be tested if hypotheses in step 1 are successfully proven. Therefore, the total 5% Type I error (alpha) can be allocated to the step 2 testing, and so on. Within each step, a parallel testing strategy is applied, i.e., the hypotheses will be tested simultaneously at a 5% alpha level (2-sided), and a successful demonstration of all hypotheses within the step is required to continue to the next step.

The following hypotheses will be tested:

#### STEP 1 - Parallel testing of $H_{01}$ and $H_{02}$

$$H_{01}: \text{Day 29 GMT}_{\text{ARCT-2303 booster dose}} / \text{Day 29 GMT}_{\text{ARCT-154booster dose}} \leq 1.0$$

$$H_{02}: \text{Day 29 SCR}_{\text{ARCT-2303 booster dose}} - \text{Day 29 SCR}_{\text{ARCT-154booster dose}} \leq -5.0\%$$

#### STEP 2 - Parallel testing of $H_{03}$ and $H_{04}$

$$H_{03}: \text{Day 29 GMT QIV}_{\text{QIV+ARCT-2303}} / \text{Day 29 GMT QIV}_{\text{QIV+Placebo}} \leq 0.67$$

$$H_{04}: \text{Day 29 GMT ARCT-2303}_{\text{QIV+ARCT-2303}} / \text{Day 29 GMT ARCT-2303}_{\text{ARCT-2303+Placebo}} \leq 0.67$$

#### STEP 3 – Sequential Testing of $H_{05}$ then $H_{06}$

$$H_{05}: \text{Day 29 SCR}_{\text{ARCT-2303 booster dose}} - \text{Day 29 SCR}_{\text{ARC-154booster}} \leq 0\%$$

$$H_{06}: \text{Day 29 GMT}_{\text{ARCT-2303 booster dose}} / \text{Day 29 GMT}_{\text{ARC-154booster}} \leq 1.5$$

See for more details, Section 10.1 of the protocol.

#### 3.3.2 Analysis of covariance

Analysis of covariance (ANCOVA) is a general linear model that evaluates whether the means of a dependent variable (DV) are equal across levels of one or more categorical independent variables (IV) and across one or more continuous variables (CV). Mathematically, ANCOVA decomposes the variance in the DV into variance explained by the CV(s), variance explained by the categorical IV, and residual variance (Keppel, G. (1991)).

The GMT ratio will be assessed using the ANCOVA model with treatment as factor and baseline antibody titer level (log-scale), age and sex as covariates, adjusted for the stratification factors from the CRF: number of previous doses and composition of last booster, if applicable. Two-sided 95% CIs for GMT ratio will be obtained by taking the anti-log of the confidence limits for

the adjusted mean difference of the logarithmically transformed assay results which is calculated using the t-distribution.

The general code to be executed in SAS for ANCOVA is as follows:

```
ODS OUTPUT LSMeanDiffCL = output_data_name;  
PROC GLM DATA=input_data;  
class Treatment Factor* sex**;  
model LogValue=Treatment Covariate# Factor* sex**/solution;  
lsmeans Treatment/pdiff cl;  
run;  
**sex as a categorical variable (Male, Female)  
#Covariate: age as a continuous variable, baseline antibody titers in log scale  
*stratification factors (not applicable when comparing the historical control group)  
1. number of previous COVID-19 vaccine doses (3 vs 4+)  
2. composition of the booster dose (original strain, bivalent/XBB1.5, unknown).
```

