May not be used, divulged, published or otherwise disclosed without written consent of Arcturus Therapeutics, Inc.

| Section Number and Name | Description of Change | Brief Rationale |
|-------------------------|--|---------------------------|
| Protocol – Table 9 | Use of stratification factors in Miettinen-Nurminen method for SCR difference specified. | Address U.S. FDA request. |
| Protocol -References | Corrected grammar and formatting. | Improve clarity. |

Protocol Amendment 2 (Version 2.0, 21 February 2024): Summary of Changes

| Section Number and Name | Description of Change | Brief Rationale |
|---|---|---|
| Throughout Protocol | Corrected spelling, grammar, and formatting. | Improve clarity. |
| Synopsis – Main Inclusion and Exclusion Criteria | Main inclusion and exclusion criteria updated to include criteria related to pregnancy, breastfeeding, and adherence to required contraception methods for individuals of childbearing potential. | To address EC recommendations and align with the protocol. |
| Synopsis – Secondary Immunogenicity Objectives Protocol - Table 4 Objectives, Endpoints, Estimands | SCR will not be performed at Day 181 (objectives #3 and #5). | Clarification. |
| Synopsis – Secondary Immunogenicity Objectives Protocol - Overall Design | Randomization will not be stratified by site. | Clarification. |
| Synopsis, Protocol - Background | Specified that the Southern Hemisphere 2024 season vaccine composition for both influenza vaccines will be used in the study. | Clarification to address RA recommendation. |
| Protocol – Randomization | Stratification included. | Alignment throughout the protocol/synopsis. |
| Protocol - Table 1 Schedule of Assessments | Timepoints for collection of blood samples for immunogenicity assessment and cardiac enzymes and for collection of AEs clarified in footnotes. | Clarification and alignment throughout the protocol/synopsis. |
| Synopsis, Protocol – Exclusion Criteria | Exclusion criteria #1 revised to specify temperature is to be measured by any method and fever is defined as temperature of $\geq 38^{\circ}\text{C}$ ($\geq 101.4^{\circ}\text{F}$). | Alignment throughout the protocol/synopsis. Provide flexibility to sites. |
| Synopsis, Protocol – Exclusion Criteria | Exclusion criteria # 5 updated to include history of severe hypersensitivity to any vaccine. | Clarification and alignment. |

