### 3.9 Subgroup Analysis

Subgroup analysis for selected parameters including immunogenicity, solicited AEs, and unsolicited AEs will be performed for the second Final Analysis.

The following subgroups will be assessed for subgroup analysis (last 2 subgroups will be used for immunogenicity data only):

- Gender: Male or Female
- Race: White and Asian
- BMI:  $<30$  and  $\geq 30 \text{ kg/m}^2$
- Country: Australia, Philippines, Costa Rica and Honduras
- Ethnicity: Hispanic or Latino, not Hispanic or Latino
- Vaccine composition of last dose: ancestral, bivalent (BA.1 or BA.5 containing)
- Number of last COVID-19 doses: 3 doses or  $\geq 4$  doses

The descriptive summaries will be presented for subgroup analysis: Groups 2a and 2b combined vs Groups 3a and 3b combined for safety data; Groups 2a and 2b combined for immunogenicity data.

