##### Continuous descriptive analysis:

Age (years)

Height (cm)

Weight (kg)

BMI (kg/m^2)

Categorical descriptive analysis:

Age Category (18-64 years, 65+ years)

Sex

Race

Ethnicity

Country (derived by using the first digit of the site number)

Similarly, the available demographic and baseline parameters will be summarized for ARCT-154 recipients (study ARCT-154-J01) too.

For study ARCT-2303-01 participants, age collected on CRF is used for the analysis, while age at the time of first vaccination is considered for study ARCT-154-J01 participants.

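### The Step 2 ANCOVA leaves out country, a baseline factor known for every participant and not balanced by design: a probably small precision gain forgone, not an error

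*SAP*

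**What the plan says.** SAP 3.3.2 gives one ANCOVA for all GMT ratios, "with treatment as factor and baseline antibody titer level (log-scale), age and sex as covariates", and "adjusted for the stratification factors from the CRF: number of previous doses and composition of last booster, if applicable". The PROC GLM code in that section carries the same terms. Neither the text nor the code has a term for country or site. SAP 8.1.3 (influenza strains) and 8.1.4 (XBB.1.5) send Objectives 3 and 4 to this model.

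Country is available without new data. SAP 3.9 lists "Country: Australia, Philippines, Costa Rica and Honduras" as subgroups, and SAP 5.3 includes "Country (derived by using the first digit of the site number") among the demographic variables.

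On allocation, SAP 2.4 says that within each age cohort "participants will be randomly assigned at a 1:1:1 ratio into three study groups", and "Randomization will be stratified based on their COVID-19 vaccination history". The amendment log in Protocol Appendix 4 agrees with this current text: "Randomization will not be stratified by site".

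Protocol 10.3 asks only for covariates and stratification factors in the ANCOVA, and Protocol 10.1 leaves the detail to the SAP. Neither document gives a reason for omitting country.

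**The concern.** Groups 1a, 2a and 3a are randomised in the same countries, but nothing in the design balances them by country. If Day 29 titres differ between countries beyond what baseline titre, age, sex and vaccination history explain, that difference stays in the residual variance and widens every Step 2 interval. Chance imbalance by country also goes uncorrected in the one trial that is run.

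What is at stake is precision. Step 2 succeeds only if all five noninferiority tests pass, and Step 3 opens only after that, so a small loss per test compounds. SAP 3.3.1 states that within a step "the hypotheses will be tested simultaneously at a 5% alpha level (2-sided"), so no alpha is divided and power per test is the quantity that matters.

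**Working it through.** **Inputs.** From SAP 13.1, Step 2: 360 evaluable per group, common SD 0.60 on the log10 scale, true GMT ratio 1.0, one-sided alpha 0.025, independence across the five tests. From SAP 8.1.3 and 8.1.4: decision limit 0.67. Assumed, because the documents give no figure: *b*, the share of variance absorbed by the planned covariates, and *R²*, the share of the remaining variance explained by country.

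**The plan's own figure.** SAP 13.1 uses a margin of 0.176. SE = 0.60 × √(2/360) = 0.04472, noncentrality = 0.176/0.04472 = 3.935, and the noncentral t with 718 df gives 0.9756 (SAP: 0.97578). The fifth power is 0.884 (SAP: 0.885). Reproduced.

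**Same calculation at the actual limit.** −log10(0.67) = 0.1739. Noncentrality = 0.1739/0.04472 = 3.889, power 0.9728 per test, and 0.9728⁵ = 0.871.

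**With country.** SE = 0.60 × √[(1 − b)(1 − R²)] × √(2/360), noncentrality = 0.1739/SE, joint power = (per-test power)⁵. With R² = 5%:

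| Planned covariates absorb (b) | Per test, no country | All five, no country | Per test, with country | All five, with country | Gain (points) |
|---|---|---|---|---|---|
| 0% | 0.9728 | 87.1% | 0.9786 | 89.7% | 2.6 |
| 10% | 0.9836 | 92.1% | 0.9875 | 93.9% | 1.8 |
| 20% | 0.9914 | 95.8% | 0.9937 | 96.9% | 1.1 |
| 30% | 0.9963 | 98.2% | 0.9975 | 98.7% | 0.5 |

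Example, b = 20%: SD = 0.60 × √0.80 = 0.5367, SE = 0.0400, noncentrality 4.348. With country, SD = 0.5367 × √0.95 = 0.5231, SE = 0.0390, noncentrality 4.461.

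**Range over R².** At b = 0, an R² of 2% gives 88.2% and 10% gives 92.1%. In interval terms, R² = 5% narrows the log-scale interval by 1 − √0.95 = 2.5%, equivalent to 360/0.95 = 379 evaluable per group. If the residual SD were 0.65, joint power would move from 76.5% to 80.3% at R² = 5%, so the term helps more if the SD has been underestimated.

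**Cost if country explains nothing.** The current model has 8 parameters (intercept, treatment, baseline, age, sex, one for doses, two for composition), leaving 720 − 8 = 712 df. Country takes 3 more, leaving 709. The standard error grows by about √(1 + 3/708) = 1.002, or 0.2%. Carried through at b = 0, joint power goes from 87.1% to about 86.9%. The table omits this inflation, so its gains are overstated by up to about 0.2 points.

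**Validity.** In a simulation (3,000 runs per setting, 720 participants, four equal countries, allocation not stratified by country), 95% interval coverage was 0.947 to 0.955 with or without the country term. One-sided error at the margin was 0.019 to 0.029, near 0.025. At R² = 10%, mean interval width fell from 0.1755 to 0.1669 log10 units.

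**The case against.** The strongest reply is that nothing is wrong with the planned model. Step 2 is randomised, so omitting country causes no bias. The model already adjusts for log baseline titre and both stratification factors, as the protocol asks, and country is not a stratification factor. Chance imbalance applies to any unlisted variable. All of this stands, and it limits the point to precision.

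It also stands that the gain has no documentary basis. The R² values are assumptions, and they must be variance beyond baseline titre, age, sex and vaccination history. The split of Cohort A across countries is not given, and a very small country would add little.

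Two stronger readings are tempting. A reader might infer that a country term is needed because five-test power at the 0.67 limit is 87.1%, below the stated 88%. That does not follow. The 87.1% is for an unadjusted t-test with the planning SD; it describes the planned ANCOVA only if its covariates explain nothing. The gap comes from rounding the margin to 0.176 in the power table, which a country term does not correct. Positive correlation between tests, plausible because all five share Group 1a and the four influenza tests use the same participants, would also raise joint power.

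A reader might also infer from SAP 3.9 that the sponsor regards country as a predictor that belongs in the model. That section lists country beside gender, race, BMI and ethnicity, for descriptive summaries at the second final analysis. For immunogenicity it covers Groups 2a and 2b combined, not the Step 2 contrasts. It shows that country is available and nothing more.

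What the objection does not remove is that the term uses data already held and costs almost nothing.

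**Conclusion.** The point holds as a minor missed efficiency. The planned Step 2 estimates are unbiased and their intervals valid. Adding country would probably narrow them slightly. If country explains 5% of residual variance, joint power for the five tests gains about 2.6 points when the planned covariates explain nothing, falling to about 0.5 points when they absorb 30%. If country explains nothing, the loss is about 0.2 points at most. These figures rest on SD 0.60, 360 evaluable per group, true ratios of 1.0, the SAP's independence assumption, and assumed values for the two variance shares.

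The point is confined to Objectives 3 and 4. In Step 1 every control comes from the Japanese study (Protocol 2.1.2), and Japan is not among the countries in SAP 3.9, so country cannot be separated from vaccine there.

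**What to change.** In SAP 3.3.2, add country (four levels, from the site number) as a class factor in the ANCOVA for Objectives 3 and 4, and keep the present model as a sensitivity analysis. State that country is not used in the Step 1 comparison or in the Step 3 tests, which use the same historical control.

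The cost is one term in the code and one sentence in the SAP. No new data are needed. Protocol 10.1 and 10.3 leave the covariate details to the SAP, so a protocol amendment does not appear necessary.

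Timing decides the role of the new term. Objectives 3 and 4 belong to the first final analysis (SAP 10.1), which the documents do not date; the latest SAP version is of 18 December 2024. If that analysis has not been run, the country-adjusted model can be primary. If it has, keep the present model as primary and report the country-adjusted result as a sensitivity analysis labelled post hoc.
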